6.3 Pharmacokinetics/pharmacodynamics

The population PK analysis and pharmacodynamic analyses may be presented separately from the CSR and will be described in a separate analysis plan.

6.3.1 Pharmacokinetics

BAY 2433334 and BAY 2826102 concentrations will be summarized per sampling interval and visit, separated according to actual dose.

The analyses will be focused on descriptive statistics. The following statistics will be calculated for each of the sampling intervals: arithmetic mean, standard deviation and coefficient of variation (CV), geometric mean, geometric standard deviation (re-transformed standard deviation of the logarithms), and CV, minimum, median, maximum value and the number of measurements.

Means at any time will only be calculated if at least 2/3 of the individual data were measured and were above the lower limit of quantification (LLOQ). For the calculation of the mean value a data point below LLOQ will be substituted by $\frac{1}{2}$ LLOQ.

Plots will be prepared by naïve pooling all individual plasma concentrations (naïve pooling) versus actual relative study times (time of sample collection after time of study drug administration, time after most recent dose) using both a linear and semi-logarithmic scale, and presented by visit and treatment. Samples which are collected outside of the predefined windows will nevertheless be valid for PK analysis.

6.3.2 Pharmacodynamics

Plots will be prepared by pooling all individual PD data (naïve pooling) versus actual relative study times (time of sample collection after time of study drug administration, time after most recent dose) using both a linear and semi-logarithmic scale, and presented by visit and treatment, for absolute values, change from baseline and ratio to baseline. Samples which are collected outside of the predefined windows will nevertheless be valid for PD analysis.

The following PD/PD correlations will be provided as scatterplots (with observed values, changes from baseline and ratios to baseline):

- aPTT versus inhibition of FXIa (AXIA)
- D-Dimer versus inhibition of FXIa (AXIA)
- D-Dimer versus aPTT

The following PK/PD correlations will be provided as scatterplots (with observed values, changes from baseline and ratios to baseline):

- aPTT versus plasma concentrations of BAY 2433334.
- inhibition of FXIa (AXIA) versus plasma concentrations of BAY 2433334.
- D-Dimer versus plasma concentrations of BAY 2433334

The following data rules apply:

- Changes from baseline = Actual value Baseline value
- Ratio to Baseline = Actual value / Baseline value

Further data-driven exploratory analyses may be applied.

For the calculation of the mean value a data point below LOQ will be substituted by one half of the limit.

6.4 Safety

6.4.1 Primary Safety

6.4.1.1 Primary Safety Estimand

The primary safety estimand is the ratio of the proportions of the composite of ISTH major and clinically relevant non-major bleeding within 3 months comparing pooled doses of BAY 2433334 and comparator drug apixaban in adult participants with AF who have taken at least one dose of study medication of BAY 2433334 or comparator drug apixaban, while the participant is alive and exposed to study intervention.

6.4.1.2 Primary Safety Analyses

The primary estimator is the ratio of incidence proportions of the primary safety endpoint observed in participants who are under treatment with BAY 2433334 (all doses pooled) and the active comparator for up to 12 weeks with corresponding 90% confidence interval.

The (crude) incidence proportion of the primary safety endpoint is defined as the number participants with an event in 12 weeks while the participant is under exposure of study drug (counting treatment according to the treatment emergent data scope) divided by the number of participants in the treatment arm who took at least one dose of study drug, (the SAF population) i.e.

 $\widehat{CI}_{A} = \frac{\#Participants \text{ with an event}}{\#Participants \text{ that took at least one dose of study drug }A}.$

These incidences proportions will be estimated for BAY 2433334 arm (all doses pooled) and the apixaban arm. The main estimator for this study is the ratio of the (crude) incidence proportions

$$\widehat{CIR} = \frac{\widehat{CI}_{BAY \ 2433334}}{\widehat{CI}_{Apixaban}}$$

The corresponding 90% two-sided confidence interval will be calculated using the Farrington-Manning score for an exact confidence interval. The calculation of the ratio of crude incidences and the confidence intervals will be done by using SAS code corresponding to the following:

Taking the time under risk into account, the exposure-adjusted incidence rate will be calculated for each treatment arm with an 90% confidence interval.

The exposure-adjusted incidence rate will be expressed a "subjects with an event – per 100 participant years". For that the following formula is used:

 $IR_{adj} = \frac{\#Participants with an event}{\sum time under treatment (in days)/(100 * 365.25)}$

The 90% confidence interval for the exposure-adjusted IR will be computed as

$$\left[\frac{IR_{adj} * \chi^2(0.05; 2e)}{2e}; \frac{IR_{adj} * \chi^2(0.95; 2e)}{2e}\right]$$

with $\chi^2(q; 2e)$ the q quantile of a chi square distribution with 2e degrees of freedoms and e the number of participants with an event. (Nelson 1982)

In addition to the main analysis, time-to-first-event analyses taking competing events into account will be performed. For that Aalen-Johansen estimates for the cause specific cumulative risk will be presented.

The competing events for the primary safety endpoint are Death (all causes) and premature discontinuation.

The cumulative incidence risk, i.e. the probability of having a specific event E at or before a timepoint t, $P(T \le t, E = 1)$, will be estimated for time-to-event endpoints by Aalen-Johansen estimators with the competing event as defined in section 6.2.

The difference of the Aalen-Johansen estimators at day 85 (week 12) between BAY 2433334 treatment and Apixaban will be presented with a 90% confidence interval.

As the Aalen-Johansen estimator is approximately normal distributed (Aalen, Borgan and Gjessing 2008), the difference of Aalen-Johansen estimators is approximately normal distributed. Thus, the two-sided 90% confidence interval is obtained via:

Page: 21 of 25:

$$\left[(\widehat{A}J^{BAY}(85) - \widehat{A}J^{Apixaban}(85)) \pm z_{0.95} \sqrt{\sigma^2(\widehat{A}J^{BAY}(85)) + \sigma^2(\widehat{A}J^{BAY}(85))} \right]$$

with $\widehat{AJ}^{TRT}(85)$ the Aalen-Johansen estimator for treatment TRT at day 85, $z_{0.95}$ the 95% quantile of the standard normal distribution and $\sigma^2(\widehat{AJ}^{TRT}(85))$ the estimated variance of the Aalen-Johansen estimator at day 85, estimated with the Aalen method.

All analyses will be done for the pooled doses of BAY 2433334 and for each of the two doses.

csHRs will be calculated for the respective event and the competing event. Gray's test of equivalence of the cumulative incidence functions, stratified by prior usage of NOAC, will be performed. The cause specific hazard ratios and the corresponding confidence intervals will be estimated on separate models for the pooled doses of BAY 2433334 and each comparison (if applicable). No comparison of the different doses of BAY 2433334 is planned.

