- participant on a NOAC in case of at least one bleeding risk feature (history of a prior bleed within the last 12 months requiring medical attention and / or moderate renal dysfunction with eGFR 30-50 ml/min and / or current clinically indicated antiplatelet therapy with acetylsalicylic acid [ASA] ≤ 100 mg).

Stratification will be based on whether participants received a NOAC before study start or were not treated with any oral anticoagulant.

The planned study duration will be 14-16 weeks, consisting of:

- Screening period (visit 1 until visit 2): 2 weeks (participants will be screened and have to be randomized within 2 weeks of screening. If all information is available, a participant can be randomized on the day of screening (visits 1 and 2 are combined).
- Treatment period (from visit 2 through visit 6 [EOT] or visit 6a [ET]): 12 weeks
- Safety follow-up (visit 7 [SFU]): 14 days (+ 7 days) after EOT or ET.

Study visits will take place as visits at the study sites and telephone calls. Visits at the study sites take place at screening and randomization (visit 1 and visit 2), at week 4 (visit 4) and week 12 (i.e. EOT, visit 6).

[figure not shown]
Telephone calls will take place at week 2 (visit 3), week 8 (visit 5), as well as 2 weeks after the EOT visit for participants who will take study intervention until the planned EOT (i.e. SFU, visit 7).

For participants who prematurely discontinue from study intervention, an early termination (ET) visit (visit 6a) will take place as soon as possible as visit at the study sites. Telephone calls take place 14 days after the ET visit (i.e. SFU, visit 7).

The study design is presented in Figure 3-1: Study design overview.

Page: 7 of 25:

Figure 3-1: Study design overview

Duration of Treatment: 12 weeks

Note: Participants receiving BAY 2433334 will also receive the apixaban matching placebo. Participants receiving apixaban will also receive the BAY 2433334 matching placebo. During the safety follow-up, further therapy (e.g. NOAC) is at discretion of the investigator.

4. General Statistical Considerations

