4.5.3 Time-to-Event variables

For the treatment emergent data scope, the time from first intake of study drug to an event is of interest. The time to an event (in days) will be derived the following:

Date of Event – Date of first study drug intake + 1.

For time to event variables in the intention-to-treat (ITT) data scope the time from randomization to an event is of interest. The time to an event (in days) will be derived the following:

Date of Event – Date of randomization + 1.

Survival functions, incidence rates and cumulative hazard calculations will be done only for endpoints with at least 3 events in at least one treatment arm. (Cause specific) hazard ratios (csHR) will be calculated only if in addition at least 1 event in each of the compared treatment arm occur.

If treatment arms are pooled the number of events needed applies on the pooled arm not on each treatment arm.

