$$\widehat{AJ_E}(t) = \sum_{t_j \leq t} \widehat{S}(t_{j-1}) (\widehat{\Lambda}_E(t_j) - \widehat{\Lambda}_E(t_{j-1})).$$

Gray's (Gray 1988) test for equivalence of the cumulative incidence functions, stratified by prior usage of NOAC, will be performed. To derive the Aalen-Johansen estimators and the test statistics with the corresponding confidence intervals, SAS program code corresponding to the following will be used:

```
PROC LIFETEST DATA = <dataset> ALPHA=0.1 ERROR=AALEN;
STRATA stratumn / GROUP=trtgrpn;
TIME ttevalue * status(0)/eventcode=1;
RUN;
/*
where
dataset = name of sub-dataset including all FAS participants randomized to
respective BAY2433334 treatment group and control group
trtgrpn = variable coding randomized antithrombotic treatment group
(0 = apixaban control group, 1 = BAY243334 treatment
ttevalue = time to first occurrence of outcome event or competing event
status = status of the participant at event time (0 = right-censored,
1 = event of interest, 2 = competing event)
stratumn = variable for NOAC stratification factor (two levels)
*/
```

Cause-specific HRs will be calculated for the respective event and the competing event. The cause-specific hazard ratios and the corresponding confidence intervals will be estimated on separate cause-specific hazard models for the comparison of the pooled doses of BAY 2433334 versus apixaban and for each treatment dose of BAY 2433334 versus apixaban (if applicable). No comparison of the different doses of BAY 2433334 is planned.

To derive the cause specific hazard ratios and the corresponding confidence intervals, SAS program code corresponding to the following will be used:

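### Does the crude bleeding risk ratio need a NOAC-stratified counterpart because allocation and Gray's test are stratified by prior NOAC use?

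*SAP*

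**What the plan says.** The estimand in SAP Section 6.4.1.1 is marginal: "The primary safety estimand is the ratio of the proportions of the composite of ISTH major and clinically relevant non-major bleeding within 3 months". It contrasts both doses together with apixaban, among participants who took study drug. Section 6.4.1.2 divides participants with an event by participants dosed in each whole arm, and then names the estimator: "The main estimator for this study is the ratio of the (crude) incidence proportions". Its interval is fixed there too: "The corresponding 90% two-sided confidence interval will be calculated using the Farrington-Manning score for an exact confidence interval". Section 6.4.1.3 carries this estimation over to the four secondary bleeding endpoints.

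The NOAC factor appears in three other places:

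- Section 3: "Stratification will be based on whether participants received a NOAC before study start or were not treated with any oral anticoagulant". The code comments in Section 6.2 call it a two-level NOAC stratification factor, so reading it as the randomisation factor is natural.
- Section 6.4.1.2, among the additional time-to-first-event analyses: "Gray's test of equivalence of the cumulative incidence functions, stratified by prior usage of NOAC, will be performed".
- Section 6.4.2, where NOAC treatment at randomisation (yes/no) is one of four subgroups with a planned comparison between arms, for the primary endpoint and for all bleeding.

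**The concern.** The usual expectation is that the analysis reflects the factors on which randomisation was stratified. Here an additional test respects the factor and the estimate that carries the main conclusion does not.

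The factor may well be prognostic. Under Section 3, participants already on a NOAC enter only with at least one bleeding risk feature, while untreated participants need none, and the endpoint is bleeding. If the strata differ in risk, two things could be at stake. The crude interval could be wider than necessary. A chance imbalance in NOAC use among dosed participants could also move the crude ratio without the reader seeing it.

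**Working it through.** **No figure to reproduce.** The SAP text gives no sample size, allocation ratio, event rate or NOAC share. All numbers below are assumptions.

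**1. Does the crude ratio target the right quantity?** Yes. The estimand is a ratio of marginal proportions and the estimator is the ratio of observed marginal proportions. The risk ratio is collapsible: if it is the same in both strata and allocation is balanced within them, the marginal ratio equals it. With strata s, events a (BAY 2433334) and c (apixaban), and arm sizes n1 and n0, the Mantel-Haenszel ratio is

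Σ(a·n0/N) / Σ(c·n1/N).

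With 2:1 allocation in every stratum, n0/N = 1/3 and n1/N = 2/3. The ratio becomes Σa/(2Σc), which is the crude ratio (Σa/500)/(Σc/250). Under balance the two estimates are identical.

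**2. What precision is lost?** Assume 250 apixaban and 500 pooled BAY 2433334, equal strata, and 4% overall apixaban risk.

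- Crude, true ratio 1: SE(log RR) = √(0.96/(0.04·250) + 0.96/(0.04·500)) = √(0.096 + 0.048) = 0.3795.
- Crude, true ratio 0.5: √(0.096 + 0.98/(0.02·500)) = √(0.096 + 0.098) = 0.4405.
- Stratified: replace p(1−p) by the mean of the stratum values. For risks of 1% and 7% this is (0.0099 + 0.0651)/2 = 0.0375 instead of 0.0384. At ratio 1 the SE is √(0.0375/(0.04²·250) + 0.0375/(0.04²·500)) = √(0.09375 + 0.046875) = 0.3750.

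| Apixaban stratum risks | Stratified SE, ratio 1 (crude 0.3795) | Stratified SE, ratio 0.5 (crude 0.4405) |
|---|---|---|
| 3% / 5% | 0.3790 | 0.4400 |
| 2% / 6% | 0.3775 | 0.4387 |
| 1% / 7% | 0.3750 | 0.4366 |

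The largest gain is 1 − 0.3750/0.3795 = 1.2%. With equal stratum risks it is zero.

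A separate simulation used 100,000 runs per scenario, 2:1 allocation with 150, 250 or 400 per arm, NOAC shares of 30 to 70%, and apixaban risks (no NOAC/NOAC) of 3/3, 2/6 or 2/12%. The SE fell by 0 to 2.2%. At a true ratio of 0.5, the chance that the upper 90% limit lies below 1 rose by at most about 2 points (largest change 38.2% to 40.0%).

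**3. Is the planned interval still valid?** Coverage by full enumeration of the 501 × 251 possible tables, from equal strata to 1%/7%:

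| Interval | Ratio 1 | Ratio 0.5 |
|---|---|---|
| Exact Farrington-Manning | 92.15% to 92.49% | 90.75% to 91.03% |
| Asymptotic score | 89.62% to 90.02% | 90.20% to 90.49% |

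The largest shift is 90.02 − 89.62 = 0.4 points. Every shift is upward, so ignoring the stratum makes the interval very slightly conservative. The width of a stratified interval was not compared with that of the exact interval.

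**4. How far can imbalance move the ratio?** A 1-point difference in NOAC share, at true ratio 1, gives 0.040/0.0398 = 1.005 (3/5%), 0.040/0.0396 = 1.010 (2/6%) or 0.040/0.0394 = 1.015 (1/7%). On the log scale, divided by 0.3795, that is 0.01 to 0.04 of one SE.

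A larger case has 240/260 on BAY 2433334 and 130/120 on apixaban (no NOAC/NOAC), a 4-point difference, with true ratio 0.50:

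- At 2/6%: 0.0204/0.0392 = 0.52. The shift is ln(0.5204/0.5) = 0.040, against a stratified SE of 0.439, or 0.09 SE.
- At 2/12%: 0.036/0.068 = 0.53. The shift is ln(0.5294/0.5) = 0.057, against 0.325, or 0.18 SE.

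**5. Do the passages contradict each other?** No. Gray's test compares cumulative incidence functions and yields no ratio. It belongs to the analyses added to the main one, and the SAP nowhere commits to stratifying every analysis.

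**The case for a change.** The best case for an addition is that the strata are selected differently on bleeding risk, so they should not be presumed equal. Two within-stratum ratios with few events each are also not one adjusted ratio, and Section 6.4.2 does not extend to ISTH major, clinically relevant non-major or minor bleeding. Specifying a stratified ratio now would avoid a post-hoc choice once an imbalance is seen.

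All of that is true, but it argues for a supportive extra and shows no fault in the plan. A Mantel-Haenszel ratio assumes a common ratio across strata, so the Section 6.4.2 comparisons show dependence on NOAC use better than it would.

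The extra also has a price. Because "All analyses will be done for the pooled doses of BAY 2433334 and for each of the two doses", one primary and four secondary endpoints over three comparisons mean up to 5 × 3 = 15 more unadjusted ratios, each an asymptotic interval beside an exact one. For rare endpoints it would often fail. At risks of 1% against 0.5%, at least one arm is empty with probability 1 − (1 − 0.99^250)(1 − 0.995^500) = 15.6%, and at 0.5% against 0.25% with 49.0%. For a single dose (250 against 250) these become 34.4% and 66.8%. Section 4.5.3 guards its hazard ratios by requiring at least 3 events in one arm, and these "will be calculated only if in addition at least 1 event in each of the compared treatment arm occur". An added ratio would need both conditions.

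Finally, Section 6.2 announces code for the cause-specific hazard ratios ("To derive the cause specific hazard ratios and the corresponding confidence intervals, SAS program code corresponding to the following will be used") that the available text does not show. A NOAC-stratified relative effect may therefore already be planned.

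**Conclusion.** The concern does not hold. The observations are correct: the main ratio is crude, the factor is stratified in the design and in Gray's test, and no combined stratified ratio appears in the visible text. None of them is a wrong statement, a contradiction or a poor choice, because the crude ratio matches the marginal estimand and its interval keeps its coverage.

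The effect is negligible under the assumptions shown: an SE 0 to 1.2% smaller (up to 2.2% in the wider range), coverage shifts of at most 0.4 points, and 0.01 to 0.04 of one SE per point of NOAC imbalance. These sizes rest on assumed sample sizes, rates and NOAC shares. The validity of the crude ratio does not depend on them.

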4.5.2 Data Scopes

Treatment emergent data scope

For the treatment emergent data scope all events from first intake of study drug up until 2 days after the last intake of study treatment will be counted. The time to event for participants with no event until 2 days after the last intake of study drug (end of data scope) will be censored at that day.

For events at the day of randomization will be counted if the time of occurrence is later than the time of first study drug intake.

This data scope will be used to handle intercurrent events according to the "while on treatment" strategy.

Intention-to-treat (ITT) data scope

For the intention-to-treat (ITT) data scope all events from randomization up until end of treatment visit (Visit 6) (end of data scope) will be counted. The time to event for participants with no event up until the end of treatment visit will be censored at that day.

This data scope will be used to handle intercurrent events according to the "treatment policy" strategy.

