6.1.1 Disposition

The following will be tabulated by treatment group and overall:

- Study sample sizes by region and country
- Study sample sizes by country and site
- Participants disposition
- Number of participants and primary reasons for screening failures
- Number of participants and primary reasons for premature discontinuation of study medication
- Number of participants and primary reasons for premature discontinuation of study follow up.

Incidences for permanent discontinuation of the double-blinded study drug and of the followup period will be provided by randomized study treatment groups, based on the case report form data.

Kaplan-Meier estimates will be used to present

- time to the date of last double-blind dose of study treatment,
- time to the date of last follow-up contact,

all calculated as days from randomization, by study treatment group.

Other details regarding visit adherence (e.g., visit completed in person, by telephone, through third party) and completion as well as study drug adherence collected via CRFs will be summarized using frequency tables by visit and study treatment group.

6.1.2 **Protocol Deviations**

No per protocol analysis set will be defined in this study. The number of participants with major protocol deviations and validity findings according to the CRF will be summarized by study treatment group as well as reasons.

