6.2 Efficacy

Efficacy analyses in this study will be exploratory only.

Exploratory endpoints for this study are:

- the composite as well as individual components of CV death, MI, ischemic stroke, • and systemic embolism,
- all-cause mortality. •

Events will be counted in the intention-to-treat data scope for the full analysis set.

The number of participants with an efficacy endpoint and percentages will be shown by treatment arm.

Taking the time under risk into account, the exposure-adjusted incidence rate will be calculated for each treatment arm with an 90% confidence interval.

The incidence rate (IR) will be expressed as "participants with an event per 100 participant years". For that the following formula (Unkel, et al. 2019) is used:

$$IR = \frac{\# Participants with an event}{\sum time \ to \ event \ (or \ censoring)(in \ days)/(100 * 365.25)}$$

The 90% confidence interval for the IR will be computed as

$$\left[\frac{IR * \chi^2(0.05; 2e)}{2e}; \frac{IR * \chi^2(0.95; 2e)}{2e}\right],$$

with $\chi^2(q; 2e)$ the q quantile of a chi square distribution with 2e degrees of freedoms and e the number of participants with an event. (Nelson 1982)

In addition, time-to-first-event analyses taking competing events into account will be performed. For that Aalen-Johansen estimates for the cause specific cumulative risk will be presented.

The competing event for the efficacy events is death or non-CV death for endpoints that include CV death. There will be no competing event for all-cause mortality.

The cumulative incidence, i.e. the probability of having a specific event E at or before a timepoint t, $P(T \le t, E = 1)$, will be estimated for time-to-event endpoints by Aalen-Johansen estimators with the competing event as defined before. For the Aalen-Johansen estimator the cumulative hazard calculated by the cause-specific Nelson-Aalen estimator is needed. The calculation of the estimators follows Allignol, Beyersmann and Schmoor (Allignol, Beyersmann and Schmoor 2016).

The cause-specific Nelson-Aalen estimator for an event E at timepoint t is calculated as:

$$\hat{\Lambda}_E(t) = \sum_{t_j \le t} \frac{\#Participants \text{ with an event } E \text{ at } t_j}{\#Participants \text{ under risk at } t_j}.$$

The Aalen-Johansen estimator takes the difference of the cause-specific Nelson-Aalen estimator into account, weighted with the Kaplan-Meier (KM) survival function, i.e. the Aalen-Johansen estimator for time t is defined as:

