6.4.1.3 Secondary Safety Analyses

The secondary safety estimands are the ratios of the proportions of participants experiencing the individual endpoints within 3 months, comparing pooled doses of BAY 2433334 and comparator drug apixaban in adult participants with AF who have taken at least one dose of study intervention (BAY 2433334 or apixaban, the comparator drug), while the participant is alive and exposed to study intervention for each of the endpoints:

- all bleeding
- ISTH major bleeding
- ISTH clinically relevant non-major bleeding
- ISTH minor bleeding.

The main analyses will follow the main estimation for the primary safety endpoint. In treatment arms with 3 or more events, in addition exposure-adjusted incidence rates and Aalen-Johansen estimators will be presented.

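### The exposure-adjusted bleeding rate in SAP 6.4.1.2 counts each participant once but, as printed, does not stop person-time at the first event

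*SAP*

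**What the plan says.** **SAP 6.4.1.2, Primary Safety Analyses.** The rate is introduced with "Taking the time under risk into account, the exposure-adjusted incidence rate will be calculated for each treatment arm". The numerator is the number of participants with an event. The denominator is the sum of "time under treatment (in days)/(100 * 365.25"). The 90% interval multiplies the rate by chi-square quantiles on 2e degrees of freedom, divided by 2e, where e is the number of participants with an event. The SAP does not define *time under treatment*.

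**SAP 6.2, Efficacy.** The lead-in, numerator and interval are the same, but the denominator is the sum of "time \ to \ event \ (or \ censoring)(in \ days)/(100 * 365.25") (as extracted from the typeset formula). Person-time there ends at the event.

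**SAP 4.5.2 and 4.5.3.** In the treatment emergent scope, bleeds count from first intake to 2 days after last intake. The censoring rule begins "The time to event for participants with no event until 2 days after the last intake of study drug" and censors on that day. Section 4.5.3 adds: "For the treatment emergent data scope, the time from first intake of study drug to an event is of interest".

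**Where the rate recurs.** For secondary bleeding endpoints, 6.4.1.3 states: "In treatment arms with 3 or more events, in addition exposure-adjusted incidence rates and Aalen-Johansen estimators will be presented". Section 6.4.1.4 says the exploratory endpoints follow the other bleeding analyses, and 6.4.2 plans exposure-adjusted rates for subgroups. None of these restates a denominator.

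**The concern.** A rate whose numerator counts each person once is a first-event rate. Its matching denominator is the time during which a first event could still occur. A participant who bleeds in week 2 and takes drug to week 12 would, on the printed formula, add about ten further weeks in which they cannot enter the numerator again. The rate then falls below the first-event rate, and the interval moves with it because both limits are multiples of the rate.

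The second gap is smaller. Bleeds are counted up to 2 days after last intake, but the formula does not say whether those 2 days are in the denominator. Two programmers could produce different values from the same data, and one report would carry two differently built rates under the name exposure-adjusted incidence rate.

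**Working it through.** The SAP gives no event rate or sample size for this rate, so there is no figure of its own to reproduce. The scaling is right: 10 participants with an event in 36,525 days gives 10 / (36525 / 36525) = 10 per 100 participant-years.

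**Inputs from the SAP.** Treatment lasts 12 weeks = 84 days (section 3). The event window runs 2 days beyond last intake (4.5.2), so the scope is S = 86 days. The interval formula is that of 6.4.1.2.

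**Assumptions, not in the SAP.** Constant hazard; everyone without an event completes 84 days on drug; event risk p over the scope of 1% to 20%; the share of bleeders who stay on drug; 250 per arm for the worked example.

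**Step 1: at-risk time.** With h = -ln(1 - p)/86, mean days from first intake to first event or end of scope are R = p/h.

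**Step 2: printed denominator, 2-day tail included.** A participant who stays on drug contributes 86 days, bleed or not. One who stops drug at a bleed on day t contributes min(t + 2, 86).

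**Step 3: relative error** = R / (mean printed denominator) - 1.

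| Risk p | R (days) | All bleeders stay on drug | Half stay | Drug stops at the bleed |
|---|---|---|---|---|
| 1% | 85.57 | -0.5% | -0.3% | -0.02% |
| 5% | 83.83 | -2.5% | -1.3% | -0.1% |
| 10% | 81.63 | -5.1% | -2.7% | -0.2% |
| 20% | 77.08 | -10.4% | -5.7% | -0.5% |

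For example, at 10% with all staying: 81.63/86 - 1 = -5.1%. Uniform event times instead of a constant hazard give almost the same: -0.5%, -2.5%, -5.0% and -10.0% if all stay.

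**Step 4: the 2-day tail.** Leaving it out shortens the denominator from 86 to 84 days and by itself raises the rate by 86/84 - 1 = 2.4%. This works against the first effect. With all bleeders staying on drug, the net errors become +1.9%, -0.2%, -2.8% and -8.2%, with the sign changing at a risk of about 4.6%.

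**Step 5: size against the interval.** With 250 per arm and all bleeders staying on drug, the printed denominator is 250 × 86 = 21,500 days with the tail and 250 × 84 = 21,000 days without it.

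| Participants with an event | At-risk days | Rate, at-risk time (90% CI) | Rate as printed, tail in (90% CI) | Rate as printed, tail out (90% CI) |
|---|---|---|---|---|
| 25 | 20,406 | 44.7 (31.1 to 60.4) | 42.5 (29.5 to 57.3) | 43.5 (30.2 to 58.7) |
| 50 | 19,270 | 94.8 (73.9 to 117.8) | 84.9 (66.2 to 105.6) | 87.0 (67.8 to 108.1) |

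Rates are per 100 participant-years. With 50 events the point estimate moves by 94.8 - 84.9 = 9.9, against an interval width of 117.8 - 73.9 = 43.9.

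**The case against.** **Total exposure may be intended.** The safety rate has its own symbol and wording, and its estimand is confined to the time a participant is alive and exposed. Dividing by full exposure can be a legitimate choice. But the SAP neither defines nor justifies it here, and the lead-in promises time under risk, as in 6.2. Intent is unclear; the mismatch between wording and formula stands.

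**Section 6.2 does not govern safety.** A reader might infer that 6.4.1.2 breaches a stop-at-event rule. The documents do not support that. The 6.2 formula is written for efficacy, on the ITT scope and full analysis set, and those differences from the safety analysis are proper. What stands is an inconsistency between two parallel formulas.

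**The end of person-time can be inferred.** A reader might say the denominator has no end at all. That goes too far: 4.5.2 names an end of the treatment emergent scope, and 6.4.1.2 invokes that scope for the crude proportion shortly before the rate. Still, the 4.5.2 rule is worded for time to event, and the rate formula does not refer to it. The mention of rates in 4.5.3 ("Survival functions, incidence rates and cumulative hazard calculations will be done only for endpoints with at least 3 events") sets a minimum event count and no denominator.

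**Section 6.1.1 is not a rival definition.** Its display of "time to the date of last double-blind dose of study treatment" might suggest that treatment time ends at the last dose. It is a Kaplan-Meier disposition summary counted from randomization and defines no treatment duration for this rate, so nothing positively supports leaving the tail out.

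**The effect is small.** This is correct for rare endpoints and is reflected in the grading.

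**Conclusion.** The point holds as a minor error in the text as written. The formula pairs a once-per-person numerator with person-time that does not stop at the first event, and it does not tie that person-time to the scope in which the bleeds are counted.

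Under the stated assumptions, with every bleeder staying on drug and the tail included, the understatement is about half the event risk. It shrinks towards zero as more bleeders stop drug. It matters mainly for frequent endpoints, possibly all bleeding or minor bleeding, and stays small against the interval widths.

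The reach is limited to supplementary per-arm rates: those for the primary endpoint and, by natural reading rather than explicit reference, those for the secondary, exploratory and subgroup bleeding analyses. A reader might infer that the main comparison is biased. It is not: the ratio of crude proportions, the Aalen-Johansen difference, Gray's test and the cause-specific hazard ratios do not use this denominator, and the SAP plans no ratio or difference of these rates.

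**What to change.** In 6.4.1.2, replace *time under treatment* with the sum of days from first intake (4.5.3) to the first event. For a participant without an event, count to the earliest of:

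- 2 days after last intake (end of the treatment emergent scope, 4.5.2);
- death;
- last study contact, if lost to follow-up;
- withdrawal of consent (4.5.4).

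State that no censoring date may lie beyond the end of that scope. A bare reference to 4.5.4 would not do: it censors a death before visit 6 at the date of death, with no cap at last intake plus 2 days. Someone who stopped drug early and died later would then contribute off-treatment time.

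Keep the safety analysis set and the treatment emergent scope. Add to 6.4.1.3, 6.4.1.4 and 6.4.2 that the same denominator applies.

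The cost is one formula line and a cross-reference. Time from first intake to event is already defined in 4.5.3 and is needed for the planned time-to-first-event analysis. No new data are required.
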